To accomplish the aims of assessing the impact of adjunctive US-guided DOT on reducing benign biopsy recommendation (i.e. FPs), while maintaining sensitivity (i.e. TPs) we will conduct a reader study of the 300 subject trial. Three of four study radiologists will serve as study readers for each case. (To eliminate potential bias a study radiologist performing the biopsy will not serve as a reader for that case.) As noted above the study radiologist who performs or supervises the US-guided DOT exam will be one of the readers. Two additional study radiologist readers will subsequently and independently review the available pre-existing patient information and CI data, (excluding the US-guided biopsy exam) and complete CI and DOT CRFs blinded to the pathology result of the abnormality that underwent biopsy. The CRFs include a BI-RADS assessment. The reader will first complete the CI CRF blinded to the US-guided DOT result, then after reviewing the optical data (tHB concentration and distribution) the reader will complete the DOT CRF including the impact of US-guided DOT information on the BI-RADS assessment, i.e. no change, decreased or increased.

Similar to the CI plus DOT workflow, for cases that have CEM, a CI CRF will be completed first, followed by a CEM specific CRF including a BI-RADS assessment and the impact of CEM on the BI-RADS assessment will be recorded. As noted above, the study radiologist that supervises the US-guided DOT and CEM exams will serve as one of the study readers. For the subsequent two readers we will alternate which adjunctive modality (i.e. CEM or US-DOT) is reviewed first and separate the subsequent review of the second adjunctive modality by a minimum of 4 weeks to prevent recollection bias).

Figure 4 diagrams the core analysis. Combined CI and US-guided DOT BI-RADS 2 and 3 assessments will be considered test negative, and BI-RADS 4A, 4B, 4C, and 5 assessments will be considered test positive. For negative tests, the biopsy proven malignant group (Gc, see Fig. 1(b)) represents false negative results, and the benign group Gd represents true negatives and reflects the potential reduction in benign biopsy recommendation if US-guided DOT were used as SOC. Ga represent true positives and Gb represent false positives utilizing adjunctive US-guided DOT. A comparison of the Ga groups i.e. CI alone vs. CI & DOT will constitute the assessment of the effect of adjunctive US-guided DOT on sensitivity.

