Up to 315 participants will be enrolled to yield 300 participants with valid US-DOT data to evaluate the primary and secondary objectives as below.

Aim 1.1 Assess the impact of US-guided DOT on potential reduction of benign biopsies
The primary objective of this prospective study is to assess the impact of US-guided DOT on the potential reduction of benign biopsies, a.k.a, improve specificity. We hypothesize that the adjunctive use of US-guided DOT will reduce the rate of benign breast biopsy. Using these criteria, the first endpoint, specificity = $Gd/(Gb+Gd)$, will be calculated as the proportion of subjects with a negative assessment (BI-RADS 2 or 3) and with no cancer at biopsy. With the exception of a small minority of patients with BI-RADS 3 assessments who elect to undergo biopsy and who will be tracked separately, all subjects in this study are considered positive using the current SOC, because they have been recommended for biopsy. Hence, 1) the specificity in this group for the SOC is 0% by definition; 2) the estimate of specificity for the DOT system represents the improvement in specificity; and 3) the estimate of specificity is also an indication of the percentage of benign biopsies that might be avoided if the NIR data were used by the radiologist in the biopsy decision making process.

Aim1.2 Assess the impact of US-guided DOT as an adjunct to CI on maintaining high sensitivity
To also ensure that the potential for false negatives is not a significant risk with the use of the US-guided DOT, we will also assess the probability of potentially misclassifying a malignant abnormality. By definition, $FN=Gc/(Gc+Ga)$, which is 1 minus sensitivity. Our earlier study [Zhu reference] indicated that both radiologists reached 96.6% to 100% sensitivity with the tHb data included, and therefore had a 0-3.4% probability of missing a malignant lesion.

All CRFs including CI, DOT, CEM and biopsy results will be entered by our study radiologists, or study coordinator or study pathologist into the OnCore data base to be exported to [name] for statistical analysis. An ad hoc analysis of the CI, CEM and optical imaging characteristics and histopathologic features of false negative cases will be performed to identify suspicious features that always indicate a level of suspicion warranting biopsy.

Aim1.3 Explore the potential benefit of managing post biopsy BI-RADS 4C and 5 lesions

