Study Hypothesis 1 for aim 1.1: The first hypothesis is that the measured tHb distribution and values can be potentially used as an adjunct for radiologists to reduce unnecessary biopsies in low risk patients with benign pathological results. The benign biopsy spare rate can be calculated as $Gd/(Gb+Gd)$ in Fig.11, which is equivalent to the specificity, the primary endpoint of Aim1.1. We observed in previous studies that specificity could be improved by 45% on average if NIR data were used in the decision-making process. Note that the specificity in this group of biopsied patients under the SOC is 0% by definition. In this study, we conservatively set the minimum acceptable specificity at 30%. The null and alternative hypotheses, which demonstrate superiority when the NIR imaging data are used as an adjunct to the diagnostic assessment versus when the SOC diagnostic data are used alone, are given by

$$H_0: \text{Specificity} \leq 30\% \text{ versus } H_1: \text{Specificity} > 30\%$$

This aim will be considered a success if the lower limit of the 95% confidence interval on specificity exceeds 30%. This hypothesis will be tested at the one-sided 0.025 level, rather than 0.05, to account for the fact that two hypothesis tests (on specificity and sensitivity) are planned. This aim is considered a success if the lower limit of the 97.5% confidence interval on specificity exceeds 30%.

Study Hypothesis 2 for aim 1.2: The second hypothesis is that, while reducing unnecessary benign biopsies, the addition of adjunct information from US-DOT still maintains a high sensitivity

in capturing nearly all malignant tumors. This can be evaluated based on sensitivity, which is calculated as $G_a/(G_a+G_c)$, as shown in Fig.11.

H_0 : sensitivity $\leq 90\%$ versus H_1 : sensitivity $> 90\%$

Based on previous study, we anticipate the sensitivity will be in the range of 96-100%. This aim is considered a success if the lower limit of the 95% confidence interval for sensitivity is at least 90%. This hypothesis will be tested at the one-sided 0.025 level, rather than 0.05, to stringently account for the fact that two hypothesis tests (on specificity and sensitivity) are planned. This aim is considered a success if the lower limit of the 97.5% confidence interval for sensitivity is at least 90%.

10.3 Sample size justifications.

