10.4 Data Analysis

All data will be analyzed as it is without imputations. Summary statistics will be used to summarize data including mean, median, standard deviation, interquartile range for continuous data and count (percentage) for categorical data.

All evaluable subjects will be analyzed. In addition to the specificity and sensitivity of US-guided DOT results, PPV, NPV, and overall accuracy will be calculated. The two study hypotheses will be tested by a binomial exact test and by constructing the one-sided 97.5% Clopper-Pearson exact confidence intervals for specificity and sensitivity. The lower limit will determine the achievement of study goals. We will explore the data further to refine the classification algorithm and the cut-off threshold. ROC analysis will evaluate the quantitatively measured tHb for pathological results of malignant biopsies. Besides tHb and its distribution, other parameters (such as oxyHb, deoxyHb, and distributions) will be either linearly incorporated with tHb to maximize the ultimate area under ROC or non-linearly through a tree-based classification model (e.g., using the R package “rpart”) (62).

The area under the ROC will be calculated to gauge the model's overall discriminative ability for biopsy results.

For the exploratory study (discordant biopsy results), the imaging data (e.g., tHb, oxyHb etc) will be summarized as appropriate in the subset of participants whose BIRAD results yield highly suspicious abnormalities (BI-RAD 4C, 5) but pathology yield benign results. Two sample t-test or Wilcoxon rank sum test as appropriate will be applied to compare this subset versus those with a malignant biopsy.

For the exploratory Study (CEM DOT correlation), we will compare BI-RADS assessments of CI&CEM vs. CI&US-guided DOT as well as correlate imaging data such as intensity of enhancement in CEM and the total hemoglobin level of US-DOT using Pearson or Spearman correlation coefficients. We will evaluate concordance/disconcordance between US-guided DOT and CEM using agreement measure (Kappa coefficient) and will test the discordance using McNemar test.

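### The two success rules do not by themselves separate added DOT information from a more lenient reading threshold, and no planned analysis sets CI&DOT against CI alone at a more lenient cut

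*Combined protocol and SAP*

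**What the plan says.** In the reader study (Section 7) each reader gives two BI-RADS assessments. "The reader will first complete the CI CRF blinded to the US-guided DOT result"; after seeing the optical data, the reader records a second assessment and whether DOT left it unchanged, lowered it or raised it. The core analysis then dichotomises the second assessment: "Combined CI and US-guided DOT BI-RADS 2 and 3 assessments will be considered test negative", with 4A to 5 positive.

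Section 7.1 (Aim 1.1) states that "the specificity in this group for the SOC is 0% by definition", because everyone was recommended for biopsy apart from a few BI-RADS 3 cases tracked separately. It concludes that "the estimate of specificity for the DOT system represents the improvement in specificity".

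Section 10.2 makes both aims single-proportion tests. For specificity, "we conservatively set the minimum acceptable specificity at 30" per cent, and "This aim is considered a success if the lower limit of the 97.5% confidence interval on specificity exceeds 30" per cent. For sensitivity, "This aim is considered a success if the lower limit of the 97.5% confidence interval for sensitivity is at least 90" per cent.

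Two other planned analyses bear on the point. Section 7 compares true positives under CI alone and CI&DOT, with no test or margin given. In Section 10.4, "ROC analysis will evaluate the quantitatively measured tHb for pathological results of malignant biopsies", alongside models with other optical values and PPV, NPV and overall accuracy.

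**The concern.** The trial asks whether optical information reduces benign biopsies. The quantity tested is how often a reader's second call falls below 4A. Two different things can lower that call: the optical data may identify benign lesions, or the reader may apply a more lenient threshold at the second read. In the second case lesions are ranked exactly as under CI and nothing has been learned, yet specificity rises from 0% by the 4A share of benign lesions.

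The design leaves room for this. The second call is a judgement: Sections 1.1 and 2 discuss a tHb threshold, but the reader-study text does not bind the call to one. The readers are study radiologists, the stated hypothesis is downgrading, and biopsy goes ahead whatever they record.

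Comparing CI with CI&DOT at the planned cut does not resolve this, because CI 4A counts as positive there. At stake is the meaning of a pass: a threshold shift and a diagnostic gain can produce the same two numbers.

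**Working it through.** **Inputs from the plan.** About 210 benign and 90 malignant lesions; limits of 30% and 90%; exact binomial tests at one-sided 2.5% with Clopper-Pearson limits; planning values of 45% specificity and 98% sensitivity (Sections 10.2 to 10.4). One result per lesion is assumed; the plan does not say how three reads become one.

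**Cut-offs and the plan's own power.**
- Specificity: 77/210 has lower limit 30.14% (pass); 76/210 has 29.69% (fail). P(Bin(210, 0.45) ≥ 77) = 99.40%, as stated in the plan.
- Sensitivity: 87/90 has lower limit 90.57% (pass); 86/90 has 89.01% (fail). P(Bin(90, 0.98) ≥ 87) = 89.33%, as stated.

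A pass on both therefore needs at least 77 benign and at most 3 malignant lesions called negative.

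**A rule with no optical input.** Call every CI 4A lesion a 3 and change nothing else. Let s_b be the share of benign lesions that are CI 4A and r the cancer rate within CI 4A. The share of cancers that are 4A is

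s_m = [r/(1 − r)] × 210 × s_b / 90,

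and the chance of meeting both rules is

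P(Bin(210, s_b) ≥ 77) × P(Bin(90, s_m) ≤ 3).

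Neither s_b nor r is in the documents, so both are assumed and varied. Example, s_b = 45% and r = 4%: s_m = (0.04/0.96) × 94.5/90 = 4.38%, giving 0.994 × 0.442 = 44%. The first factor is 0.330 at s_b = 35%, 0.855 at 40%, 0.994 at 45% and essentially 1 above that.

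| 4A share of benign | r = 2% | 4% | 6% | 8% | 10% |
|---|---|---|---|---|---|
| 35% | 31% | 21% | 10% | 4% | 1% |
| 40% | 77% | 46% | 18% | 5% | 1% |
| 45% | 87% | 44% | 14% | 3% | 0.5% |
| 50% | 83% | 36% | 9% | 1.5% | 0.2% |
| 55% | 79% | 28% | 6% | 0.7% | 0.1% |

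**Expected counts.** With 100 CI 4A lesions of which 3 are malignant, the rule gives 97/210 = 46.2% and 87/90 = 96.7%: both pass. With 5 malignant it gives 95/210 = 45.2% and 85/90 = 94.4%: sensitivity fails.

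**The planning point.** If 4A held 45% of benign and 2% of malignant lesions, the rule would have exactly the plan's design values, 45% specificity and 98% sensitivity, and would pass both with probability 0.9940 × 0.8933 = 89%.

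**Downgrading at random.** At a 37% rate in all lesions, the chance of meeting the sensitivity rule is about 2 × 10⁻¹⁴.

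**The case against.** The sensitivity rule is a real barrier. Allowing only 3 missed cancers, it blocks random downgrading outright and usually blocks relabelling of 4A once the cancer rate there exceeds about 5%. The 4A mix that makes relabelling succeed is not in the documents. This stands, and it limits the size of the concern.

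The plan also looks beyond the 4A cut. The tHb ROC in Section 10.4 does not depend on reader leniency, and worthless optical values would show up there. So it would be wrong to infer that DOT is judged only at that cut; this is true of the success rules, not of the whole plan. But that ROC does not test what tHb adds to the CI assessment: tHb could discriminate on its own and still tell the reader nothing new. The comparison of true positives shows sensitivity lost, not information gained, and PPV, NPV and accuracy are not specified against CI at a more lenient cut.

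Finally, readers are trained on optical patterns, commit their CI assessment first, are blinded to pathology and may record no change or an increase. Nothing in the documents suggests they will relabel every 4A lesion. That stands too: the rule is a benchmark, not a forecast.

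**Conclusion.** The concern holds in a limited form. The success rules have no CI-only comparator other than a 0% that follows from the cut-off, so a pass does not by itself distinguish DOT information from a shift in threshold. How easily a shift alone could pass depends on an unknown mix: likely if 4A holds at least about 40% of benign lesions with a cancer rate of 2% to 3%, less than even at 4%, unlikely at 6%, and about 1% or less at 10%. At a 35% share it is at most 31% over the rates shown.

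A reader might go further and infer that a pass could never be attributed to DOT, or that the readers will in fact relabel. The documents support neither. The paired CI and DOT forms contain what is needed to examine attribution; what is missing is the analysis. The hypotheses and sample size are not in question.

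**What to change.** Keep Hypotheses 1 and 2. Add to the core analysis (Section 7) and Section 10.4, before the reads are analysed against pathology:

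- **(a)** Per reader, sensitivity and specificity of CI alone with 4A counted as negative, beside CI&DOT at the planned cut, with paired differences and confidence intervals. Report the CI BI-RADS mix by pathology.
- **(b)** Within CI 4A and, separately, within CI 4B, the proportion downgraded to 2 or 3 among benign and among malignant lesions. Optical information should produce more downgrading in the benign; a uniform shift would not.

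In Section 7.1, replace the statement equating the whole specificity estimate with the improvement due to DOT. Say that the gain is interpreted as a DOT effect in light of (a) and (b).

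A paired comparison of reader ROC areas may be reported descriptively but should not be a pass/fail gate. If 4A holds 45% of benign and 2% of malignant lesions, a DOT that sorted 4A perfectly and changed nothing else would raise the area by only 0.5 × 0.45 × 0.02 = 0.0045. With 2 or 3 cancers in 4A, a bootstrap over the 90 cancers omits all of them in (88/90)^90 = 13% or (87/90)^90 = 4.7% of draws, so the lower two-sided 95% percentile limit would be 0. A gate would reject a real gain.

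The cost is SAP wording and some extra analysis of data already collected, with no new reads or patients. Cancers in 4A may be few, so (b) may be imprecise on the malignant side. The sponsor also accepts a possibly less favourable attribution to DOT.

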7.1 Data Analysis and Validation

US-guided DOT database and Training:

Part 1 - Using typical tHb levels and features (e.g. peripheral enhancement, shadowing) from biopsy proven benign and malignant cases obtained from earlier studies we will train the four study radiologists. The goals of the training are to familiarize the study radiologists with US-guided DOT imaging and typical hemoglobin distributions (tHb, oxyHb, deoxyHb) of different benign and malignant disease processes and to assess intra- and inter-observer variability. Data from the training study will not be used in the primary analysis.

Part 2 - Approximately 20 patients will be enrolled for the training phase. Inter-reader agreement will be assessed based on Fleiss's Kappa coefficient across the three radiologists and Cohen's Kappa between two radiologists, each associated with 95% confidence interval. The 20 patients will provide 83.32% power for testing agreement between two readers using the Kappa statistics to detect a true Kappa value of ≥ 0.75 against an unacceptable Kappa value of ≤ 0.3 , based on 1-sided normal test at a 0.1 level.

Intra-observer variability will also be assessed in the training phase. Each radiologist will read each patient's images twice (or even three times). After the first round of reading, the patients' images will be stored and the radiologists will be asked to review the same patients' images some time later, after the image orders have been perturbed and patient ID and previous evaluation results have been blinded. Integrating data from repeated evaluations from multiple radiologists on the 20 patients, generalize linear mixed effects model will be used to fit the reading results to characterize inter- and intra-reader variability based on an intra-class correlation coefficient (ICC). If a persistent large intra-reader variability is found (e.g., with $ICC > 0.3$), we will perform a focused interview with the radiologists to identify possible factors yielding inconsistency in reading results. Considering the influential factors, we will revise the training phase by providing more structured instructions illustrated with imaging examples to clarify potential issues. We expect improvement with structured instruction, but if intra-reader variability persists, we will consider requiring

repeated evaluations from the same radiologist on the same patient in order to robustly evaluate the diagnosis of US-guided DOT.

Up to 315 participants will be enrolled to yield 300 participants with valid US-DOT data to evaluate the primary and secondary objectives as below.

Aim 1.1 Assess the impact of US-guided DOT on potential reduction of benign biopsies
The primary objective of this prospective study is to assess the impact of US-guided DOT on the potential reduction of benign biopsies, a.k.a, improve specificity. We hypothesize that the adjunctive use of US-guided DOT will reduce the rate of benign breast biopsy. Using these criteria, the first endpoint, specificity = $Gd/(Gb+Gd)$, will be calculated as the proportion of subjects with a negative assessment (BI-RADS 2 or 3) and with no cancer at biopsy. With the exception of a small minority of patients with BI-RADS 3 assessments who elect to undergo biopsy and who will be tracked separately, all subjects in this study are considered positive using the current SOC, because they have been recommended for biopsy. Hence, 1) the specificity in this group for the SOC is 0% by definition; 2) the estimate of specificity for the DOT system represents the improvement in specificity; and 3) the estimate of specificity is also an indication of the percentage of benign biopsies that might be avoided if the NIR data were used by the radiologist in the biopsy decision making process.

Aim1.2 Assess the impact of US-guided DOT as an adjunct to CI on maintaining high sensitivity
To also ensure that the potential for false negatives is not a significant risk with the use of the US-guided DOT, we will also assess the probability of potentially misclassifying a malignant abnormality. By definition, $FN=Gc/(Gc+Ga)$, which is 1 minus sensitivity. Our earlier study [Zhu reference] indicated that both radiologists reached 96.6% to 100% sensitivity with the tHb data included, and therefore had a 0-3.4% probability of missing a malignant lesion.

All CRFs including CI, DOT, CEM and biopsy results will be entered by our study radiologists, or study coordinator or study pathologist into the OnCore data base to be exported to [name] for statistical analysis. An ad hoc analysis of the CI, CEM and optical imaging characteristics and histopathologic features of false negative cases will be performed to identify suspicious features that always indicate a level of suspicion warranting biopsy.

Aim1.3 Explore the potential benefit of managing post biopsy BI-RADS 4C and 5 lesions
From a total of 300 patients who undergo the US-DOT exam, we expect to recruit a small subset of patients with BI-RADS 4C or 5 lesions whose biopsy results are benign. We will correlate initial biopsy results, optical data and gold standard final pathology for this subset of patients. This pilot data will allow us to assess the potential benefit of US-guided DOT in managing discordant abnormalities, i.e. reducing additional invasive procedures of a subset of benign abnormalities.

Exploratory Aim 1.4 Explore and compare US-guided DOT and CEM
In this exploratory aim, we will evaluate the agreement (Kappa coefficient) of US-guided DOT and CEM, as both modalities measure alterations in lesion vascularity. We will compare BI-RADS assessments of CI&CEM vs. CI&US-guided DOT as well as correlate imaging data such as intensity of enhancement in CEM and the total hemoglobin level of US-DOT.

Alternative plan: *If US-guided DOT is not comparable with CEM we will evaluate the capability of US-guided DOT in improving the accuracy of combined CI&CEM because CEM may become SOC in a significant subset of patients.*

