1. STUDY OVERVIEW

1.1. Significance of Breast Cancer Diagnosis

Breast cancer is a heterogeneous disease with different histologic subtypes composed of different grades, growth rates, and metabolic activity levels resulting in a wide range of functional differences (1). Additionally, benign breast disease encompasses a heterogeneous group of lesions that vary in vascular content, proliferative index, and metabolic activity, all of which may or may not be associated with future risk of breast cancer (2). X-ray mammography is routinely used for breast cancer screening and diagnosis. Ultrasound (US) of the breast is frequently used as a complement to mammography and breast MRI (3), and may aid in screening dense breasts (4-5). Contrast enhanced mammography (CEM) is an FDA approved emerging technology indicated for lesion evaluation, determination of malignancy extent, neoadjuvant treatment response and as a substitute to MRI for high risk screening (6-9). While the characteristics of malignant and benign breast lesions are well established by conventional imaging techniques (10-12), the overlapping appearances of malignant and benign abnormalities result in hundreds of thousands of unnecessary biopsies, i.e. biopsies yielding benign results. (13) The positive predictive value of a screen detected abnormality recommended for biopsy is just over 25%, resulting in nearly 75% of unnecessary biopsy recommendations (14). An optical tomography system that adds functional information like tumor related hemoglobin concentration may improve the accuracy of the breast US exam. In particular, total Hemoglobin (tHb) values falling below a minimum value in the setting of a low or moderate suspicion abnormality (Breast Imaging and Database System, BI-RADS 4A or 4B assessment) may allow the diagnostic radiologist to downgrade the assessment to probably benign or benign (BI-RADS 3 or 2) and thereby reduce the rate of benign biopsies. In a previous study when a minimum threshold value of $tHb < 50\mu m$ was used 45% of BI-RADS 4A and 4B abnormalities that subsequently were proven to be benign could have safely avoided biopsy [34]. At this point in time we have accrued and preliminarily analyzed results from 35 patients (In addition to the initial 20 patients, 15 patients from phase 2 were also analyzed). When using $tHb < 50\mu m$ as a minimum threshold 12 patients with BI-RADS 4A or 4B abnormalities could be downgraded to a probably benign assessment and could have avoided biopsy, suggesting a 35% (12/35) reduction in benign biopsies.

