5 STUDY PROCEDURES

The study will ensue in two phases: phase 1 – training set, and phase 2 prospective trial.

The first 20 patients undergoing US-DOT will comprise the training set to accomplish the aims of:

- 1) assessing US-DOT data,
- 2) assessing intra-observer variability in the assessment of US-DOT data
- 3) assessing inter-observer variability in the assessment of US-DOT data.

For phase 2, the prospective trial, up to 315 patients will be recruited with the expectation that approximately 5% will not successfully complete the study so that 300 patients will have valid US-DOT data for the ensuing reader study.

The study flow chart that integrates US-guided DOT collection into the standard of care (SOC) clinical workflow is shown below (figure 3). SOC clinical workflow includes review of patient information and diagnostic information, such as conventional imaging results with BIRADS

[figure not shown]
assessments. The study coordinator will approach eligible patients prior to biopsy to assess their willingness to participate in the study. Patients that are willing to participate will sign informed consent and undergo US-guided DOT imaging before biopsy. A subset of patients will also undergo CEM.

Breast radiologist coinvestigators will perform (or supervise certified breast US technologists) in all NIR/US studies. As noted above, they will not be blinded to any clinical data. The function of the imaging specialist in US guided DOT imaging is to ensure that the correct anatomic location of the index lesion is imaged.

[figure not shown]
The study radiologist that performs/supervises the US-guided DOT imaging will complete CI and US-guided DOT case report forms (CRFs) blinded to the pathology result of the ensuing biopsy. In the event that the patient also undergoes CEM the study radiologist will complete CI and CEM CRFs blinded to the pathology result of the ensuing biopsy. Details of CRF completion and related reader study are noted in section 7 – Data Collection and Analysis below.

Figure 3. Study work flow

Training Set:

Prospective Trial

6. US and OPTICAL IMAGING

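### The example cut for large intra-reader variability (ICC above 0.3) points the wrong way, and the plan does not define its ICC

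*Combined protocol and SAP*

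**What the plan says.** Section 5 lists "assessing intra-observer variability in the assessment of US-DOT data" as one of three aims of the training set. Section 7.1 (training, Part 2) has each radiologist read the images of about 20 patients two or three times, and fits a generalized linear mixed model "to characterize inter- and intra-reader variability based on an intra-class correlation coefficient (ICC"). One coefficient, without a formula, serves both purposes.

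The action rule follows: "If a persistent large intra-reader variability is found (e.g., with $ICC > 0.3"), the radiologists are interviewed "to identify possible factors yielding inconsistency in reading results", and the training is then revised. The last step is conditional: "but if intra-reader variability persists, we will consider requiring" repeat evaluations by the same radiologist.

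Section 7.1 does not state the random effects, the outcome scale, or the numerator and denominator of the ICC. Section 10.1 only refers back to the training text, and section 10.4 does not mention the ICC.

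**The concern.** An ICC is a coefficient of agreement or repeatability, so high values are good. The rule treats a value above 0.3 as a sign of large variability. Read literally, it sends consistent readers to interview and lets inconsistent readers through to the reader study.

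This is the only number attached to acting on intra-reader variability. The radiologists being trained are also those who read the trial cases: "Three of four study radiologists will serve as study readers for each case". Their BI-RADS assessments define test positive and test negative. What is at stake is the training checkpoint and whether repeat evaluations are considered.

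**Working it through.** **Reproducing the plan's figure.** The 0.3 cut comes with no derivation, so there is nothing to reproduce. The only calculated figure in that part of section 7.1, the 83.32% kappa power, is recovered with 70/30 marginals (an assumption suggested by the 210/90 benign/malignant split in section 10.3) and is not in question.

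**Direction.** Split the total variance T of a reading into patient P, reader R, patient-by-reader PR and within-reader repeat error E. Intra-reader variability is E.

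| Ratio | Formula | As E rises, other components fixed |
|---|---|---|
| Same-reader ICC, readers random | (P+R+PR)/T = 1 − E/T | falls |
| Same-reader ICC, readers fixed | (P+PR)/(P+PR+E) | falls |
| Inter-reader ICC | P/T | falls |
| Reader-clustering share | R/T | falls |
| Error share | E/T | rises |

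With the first form, E/T = 0.05 gives ICC 0.95, which meets the cut. E/T = 0.85 gives ICC 0.15, which does not. Only the last row makes *above 0.3* point the right way, and it is 1 minus an ICC, not an ICC. A high R/T would indicate differences between readers, not within them.

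**How far the possible repairs differ.** Inputs: 20 patients and 2 reads (section 7.1); normal scores and a single ANOVA estimate (assumed). For one reader with true same-reader ICC ρ, the estimate is (MSB − MSW)/(MSB + MSW), where MSB and MSW are the between-patient and within-patient mean squares. It is below c exactly when MSB/MSW < (1+c)/(1−c). Since MSB/MSW is distributed as [(1+ρ)/(1−ρ)] × F(19,20),

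P(ICC < c) = P( F(19,20) < [(1+c)/(1−c)] × [(1−ρ)/(1+ρ)] ).

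At ρ = 0.5 and c = 0.3 the bound is (1.3/0.7) × (0.5/1.5) = 0.619, giving 0.151. At c = 0.7 it is (1.7/0.3) × (0.5/1.5) = 1.889, giving 0.917.

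| True ICC | As written: ICC > 0.3 | Repair A: ICC < 0.3 | Repair B: error share > 0.3 (ICC < 0.7) |
|---|---|---|---|
| 0.1 | 18% | 82% | 99.9% |
| 0.5 | 85% | 15% | 92% |
| 0.75 | 99.7% | 0.3% | 32% |

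Pooling four readers, treated as fixed, sharpens the contrast (20,000 simulated trials; reproducible variance assumed 80% patient, 20% patient-by-reader):

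| True ICC | As written | Repair A | Repair B |
|---|---|---|---|
| 0.1 | 3% | 97% | 100% |
| 0.5 | 96% | 4% | 99% |
| 0.75 | over 99.9% | under 0.1% | 26% |

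At true ICC 0.5, splits of 100/0 to 50/50 give 3% to 6% for A and about 99% for B. Three readers give about 6% and 98%. Cutting the scores into six categories (assumed shares) gives 7% and 99.7%.

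**The case against.** The strongest reply is that the number does not act alone. It follows an *e.g.*, and the words around it (large variability, inconsistency, variability that persists) all point the right way. A sensible study team would follow the words. The consequences are also contained: "Data from the training study will not be used in the primary analysis", the ICC plays no part in the hypotheses or the analysis section, and the final step is only something to be considered. The training phase also looks complete, since section 1.1 reports "In addition to the initial 20 patients, 15 patients from phase 2 were also analyzed". All of this stands, and it limits the point to a minor one. It does not make an example that contradicts its own sentence correct.

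Second, the plan's own kappa benchmark, 0.3 or less being unacceptable, suggests a slip for ICC below 0.3. That makes repair A the likelier intent but does not settle it, because kappa there concerns agreement between readers and the ICC is undefined. A reader share R/T is a third conceivable origin of the figure; in that case the label as well as the cut would need correcting.

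Third, the percentages rest on assumed inputs and compare repairs that the plan does not state. That is fair: they show why the choice must be explicit and do not measure harm to the trial.

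**Conclusion.** The concern holds and is minor. The direction error follows from the definition of the usual ICCs and needs no simulation. The missing definition is a matter of record: no section supplies it. The documents do not settle which rule was intended, and the choice matters: at true ICC 0.5 the two main candidates fire 15% and 92% of the time for one reader, and 4% and 99% pooled over four.

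Those percentages assume normal scores, two reads, 20 patients and a single estimate. They do not model the planned generalized mixed model or the requirement that variability be persistent. No effect on specificity, sensitivity, power or type I error is shown. If training is finished, the open question is which direction was applied.

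**What to change.** State the cut together with its formula, and choose one meaning explicitly:

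- If a same-reader ICC is meant, trigger when it falls **below** a stated floor (0.3, or a higher value that the sponsor justifies).
- If 0.3 was meant as the within-reader error share, call it that: error share above 0.3, equivalent to ICC below 0.7.

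Define the intra-reader and inter-reader ICCs separately, and state the outcome scale. Then confirm which direction was applied to the training readings and whether the decision on repeat evaluations still stands.

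As a preference rather than a requirement, compute the intra-reader ICC per reader or with readers fixed, as (P+PR)/(P+PR+E), and report both ICCs with confidence intervals. This keeps systematic differences between readers from counting as repeatability. For example, with P = 0.2, R = 0.6, PR = 0 and E = 0.8, including R gives 0.8/1.6 = 0.50, while the per-reader value is 0.2/1.0 = 0.20.

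The cost is a one-line correction with a definition, no change in sample size, and at most one refit of the planned model if the repeat readings were kept, which the documents do not confirm.
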